6.1. Multiple Imputations of Missing Data

Multiple imputation of binary variables: The MI procedure replaces each missing binary response value with a set of plausible values that represent the uncertainty about the right value to impute. Twenty imputed datasets will be generated based on logistic regression models. These multiple imputed data sets are then analyzed by using the same method for the primary analysis for complete data as specified in Section 6.3. The results from each set of imputed data sets will then be combined using Rubin's rule {Rubin 1987}. Stratification factors will be included in the imputation model.

Multiple imputation of continuous variables: All subjects with baseline measurement will be included. The MI procedure replaces each missing value with a set of plausible values that represent the uncertainty about the right value to impute. Twenty imputed datasets will be generated based on linear regression models on observed values. These multiple imputed data sets are then analyzed by using the analysis method specified in Section 6.4 for complete data. The result of each imputed data set will be combined using Rubin's rule {Rubin 1987}. Stratification factors and baseline values will be included in the imputation model as covariates.

6.2. Definition of the Primary Efficacy Endpoint

The primary endpoint is the proportion of subjects fulfilling protocol-specified response criteria at Week 12, as compared to baseline.

Response is defined as follows (also see [Appendix 2](#)):

- For subjects with elevated hsCRP (defined as $\text{hsCRP} \geq 1.5$ upper limit of normal [ULN]) on Day 1, response is defined as achieving all of the following:
 - $\geq 20\%$ improvement in hsCRP
 - $\geq 20\%$ improvement in at least 3 out of 5 subject reported, SjS related visual analog scales (VAS; subject's assessment of global disease, pain, oral dryness, ocular dryness, and fatigue)
 - no worsening (i.e., no increase >30 mm from baseline) in any of the above VAS
- For subjects without elevated hsCRP ($\text{hsCRP} < 1.5$ ULN) on Day 1, response is defined as achieving all of the following:
 - no increase in hsCRP to ≥ 1.5 ULN
 - $\geq 20\%$ improvement in at least 3 out of 5 subject reported, SjS related VAS (subject's assessment of global disease, pain, oral dryness, ocular dryness, and fatigue)
 - no worsening (i.e., no increase >30 mm from baseline) in any of the above VAS

6.3. Analysis for the Primary Efficacy Endpoint

6.3.1. Primary Analysis of Primary Endpoint

In the primary analysis, the primary outcome in each active treatment group will be compared to the outcome in the placebo group using a superiority test at the 2-sided 0.05-level. The following null hypotheses will be tested (vs. the respective alternative hypotheses):

- H01: There is no difference in the responder rate between filgotinib 200 mg group and placebo group at Week 12
- H02: There is no difference in the responder rate between lanraplenib 30 mg group and placebo group at Week 12
- H03: There is no difference in the responder rate between tirabrutinib 40 mg group and placebo group at Week 12

The analyses will be performed using Cochran Mantel Haenszel (CMH) test adjusted for the randomization stratification factors. If CMH test stratified by both stratification factors is not appropriate due to small cell counts then the levels of the stratification by ESSDAI scores will be pooled, and the analysis will be stratified only by use of concurrent immunomodulatory drugs at baseline. Each of the three hypotheses will be tested separately at the 2-sided, 0.05-level.

The primary analysis will be based on the Treatment Policy Estimand, with missing values imputed by multiple imputation method described in Section 6.1.

The number and percentage of responders in each treatment group as well as 95% confidence intervals (CIs) will be presented for each visit.

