8.5. Efficacy Analysis

8.5.1. Primary Analysis

The primary endpoint is the proportion of subjects fulfilling response criteria (as outlined in Section 2). The primary analysis will consist of a superiority test of each of filgotinib, GS-9876 or GS-4059 compared to placebo, respectively. CMH approach adjusting for the randomization stratification factors will be used for the hypothesis testing at the 2-sided 0.05-level.

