3.3. Strata and Covariates

Subjects will be randomly assigned to treatment groups via the interactive web response system (IWRS) in a 1:1:1:1 ratio using a stratified randomization schedule. Stratification will be based on the following variables:

- Use of concurrent immunomodulatory drugs at baseline (Y/N: conventional synthetic disease modifying antirheumatic drugs (csDMARD[s]) or corticosteroids)
- Hematologic + biological component scores of the ESSDAI obtained at screening (combined score of <2 or ≥ 2)

Only systemic use of csDMARDs (route of administration oral, subcutaneous, intramuscular, or intravenous) is considered for the stratification. If there are discrepancies in stratification factor values between the IWRS and the clinical database, the values recorded in the clinical database will be used for analyses. If it is impossible to derive the stratification factor from the clinical database due to missing values, data from IWRS will be used.

Efficacy endpoints will be evaluated using stratification factors as covariates or stratification variables for analyses, as specified in Section 6.

For efficacy endpoints, the baseline value of the efficacy variable(s) will be included as a covariate in the efficacy analysis model.

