3.4. Examination of Subject Subgroups

The primary and secondary efficacy endpoints will be examined using the following baseline characteristics and randomization stratification variables:

- Age (< 50 years and ≥ 50 years)
- Diagnosis of autoimmune disease (Yes and No)
- Diagnosis of SLE (Yes, No)
- Diagnosis of RA (Yes, No)
- Duration of the disease (<5 years, ≥ 5 years)
- Use of concurrent immunomodulatory drugs (csDMARD or corticosteroids) at baseline (systemic use of these medications at Day1 – Yes and No)
- Hematological + biological component scores of the ESSDAI obtained at screening (combined score of <2 and ≥ 2).
- ESSDAI at Baseline (<14 and ≥ 14)

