6.3.2. Sensitivity Analysis of Primary Endpoint

The following sensitivity analyses of the primary endpoint will be performed:

- Using composite estimand
- Using hypothetical estimand

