6.4.2. Analysis Methods for Secondary Efficacy Endpoints

Each secondary endpoint will be analyzed using a mixed-effect repeated measures (MMRM) model with treatment, randomization stratification factors, visit, treatment-by-visit interaction as fixed effects, subjects as a random effect, and the respective baseline value (ESSDAI or ESSPRI) as a covariate. The Kenward-Roger method will be used to estimate the degrees of freedom. Each of the four endpoints will be tested separately at the 2-sided 0.05 level. The unstructured (UN) variance-covariance matrix of repeated measures will be considered first. If a model does not converge, then ARH(1) structure will be applied.

For each secondary endpoint, adjusted means (LS means) and 95% confidence intervals (CIs) obtained from the model will be presented for Weeks 12 and Week 24 time points.

Missing data will be handled using the method described in [Table 3](#).

The inferential analyses of the secondary endpoints will be based on the treatment policy estimand (main analysis of each secondary endpoint). Sensitivity non-parametric analyses of the secondary endpoints will be performed on rank-transformed data utilizing ANCOVA models with treatment group and stratification factors as effects and the rank-transformed baseline value as a covariate.

In addition, secondary efficacy analyses will be repeated for the hypothetical estimand and composite estimand.

Descriptive statistics (n, mean, SD, median, Q1, Q3, minimum, and maximum) will be presented by visit and treatment group, overall and for the subgroups listed in [section 3.4](#).

Line plots for median (Q1, Q3) change from baseline, mean (+/- 95% CI) change from baseline, and adjusted mean (LS mean) change from baseline (+/- 95% CI) will be provided for ESSDAI total score, ESSPRI total score and its components.

In addition, the box plots for ESSDAI total score and ESSPRI total score and change from baseline will be presented by visit and treatment group.

A cumulative plot of change from baseline in ESSDAI total score and in ESSPRI total score at Week 12 and Week 24 will be presented by treatment group.

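### Day 1 hsCRP status decides which hsCRP criterion a subject must meet, but the binary imputation model does not name it: a cheap, low-severity improvement

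*SAP*

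**What the plan says.** **Endpoint.** Under SAP 6.2, a subject at or above 1.5 ULN on Day 1 needs at least a 20% fall in hsCRP. A subject below 1.5 ULN needs only "no increase in hsCRP to ≥ 1.5 ULN". The VAS criteria are the same for both groups. SAP 5.2 already categorises baseline hsCRP at 1.5 ULN.

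**Primary test.** SAP 6.3.1: "The analyses will be performed using Cochran Mantel Haenszel (CMH) test adjusted for the randomization stratification factors". Protocol 8.5.1 agrees: "CMH approach adjusting for the randomization stratification factors will be used for the hypothesis testing at the 2-sided 0.05-level". The two factors are immunomodulatory drug use and the ESSDAI hematologic plus biological score; neither contains hsCRP.

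**Imputation.** Missing responses are multiply imputed by logistic regression. For the binary endpoint, SAP 6.1 says "Stratification factors will be included in the imputation model" and names no other term. For continuous endpoints the same section names stratification factors and baseline values.

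**Other analyses of the primary endpoint.** SAP 6.3.2 ("The following sensitivity analyses of the primary endpoint will be performed") lists only the composite and hypothetical estimands. SAP 3.4 ("The primary and secondary efficacy endpoints will be examined using the following baseline characteristics and randomization stratification variables") does not list hsCRP. Protocol 8.5.2 and SAP 6.5 are redacted.

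**General covariate sentence.** SAP 3.3: "For efficacy endpoints, the baseline value of the efficacy variable(s) will be included as a covariate in the efficacy analysis model". The secondary-endpoint model carries this out with "the respective baseline value (ESSDAI or ESSPRI) as a covariate". SAP 6.3.1 has no covariate.

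**The concern.** hsCRP status is more than an ordinary baseline covariate here, because it selects the rule a subject must pass. If the two rules differ in difficulty, response rates will differ by hsCRP group. An imputation model that ignores the status then gives a missing elevated subject the same chance of response as a missing non-elevated subject in the same arm and strata.

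That matters only if missingness also depends on hsCRP, and differently by arm. Any one missing VAS makes the response missing (SAP Appendix 2). The hypothetical estimand sets further data to missing (SAP Table 3), so the same model serves two analyses.

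At stake are a small shift in the estimated risk difference, a little precision, and a view of whether an effect holds under both hsCRP rules.

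**Working it through.** **The plan's own figure.** 70% vs 30%, 2-sided 0.05, 85% power, 35 per arm (SAP 1.3). With pooled variance, n = [1.96·√(2·0.5·0.5) + 1.036·√(0.21 + 0.21)]² / 0.4² = (1.386 + 0.672)² / 0.16 = 26.5, so 27 per arm. Power at 35 is 93.5%. The stated 35 is not reproduced, but it errs on the safe side and this point does not rest on it.

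**Assumed inputs.** The documents give no share with elevated hsCRP (π), no response gap between hsCRP groups and no missing rates. Assumed here: π = 20–40% (30% central), gap 0–20 points, overall missingness in the table below 10–19%. Arm is assumed to be in the imputation model; SAP 6.1 does not name it.

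**Closed form.** Let m0 and m1 be one arm's missing rates in non-elevated and elevated subjects. Without hsCRP, missing responses are imputed at about the arm's completer rate, so the arm's rate moves by

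shift = gap × [π − π(1−m1) / (π(1−m1) + (1−π)(1−m0))].

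- π = 30%, gap 20, 5% vs 25% missing: elevated share among completers = 0.225/0.890 = 25.3%; shift = 20 × (0.300 − 0.253) = 0.94 point.
- 10% vs 40% missing: 0.180/0.810 = 22.2%; shift = 1.56 points.
- For π from 20% to 40%: 0.70–1.10 and 1.14–1.85 points.

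The sign reverses if the dependence is in the placebo arm. Equal dependence in both arms cancels.

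**Simulation.** 15,000 trials per row, four arms of 35, π = 30%, gap 20, 20 imputations, 4-stratum CMH pooled by Rubin's rule. Entries are mean risk differences in points; missing rates are non-elevated/elevated.

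| Response rates (true difference) | Missingness | Without hsCRP | With hsCRP | Absolute error, without → with |
|---|---|---|---|---|
| 55 vs 30 (25) | 10%, unrelated to hsCRP | 24.98 | 24.96 | 0.02 → 0.04 |
| 55 vs 30 (25) | 5/25% in both arms | 24.73 | 24.51 | 0.27 → 0.49 |
| 55 vs 30 (25) | active 5/25%, placebo 11% | 25.52 | 24.57 | 0.52 → 0.43 |
| 55 vs 30 (25) | active 10/40%, placebo 19% | 26.33 | 24.75 | 1.33 → 0.25 |
| 70 vs 30 (40) | active 10/40%, placebo 19% | 40.94 | 39.33 | 0.94 → 0.67 |
| 30 vs 30 (0) | active 10/40%, placebo 19% | 1.65 | 0.22 | 1.65 → 0.22 |

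A separate simulation gave 1.97 without and 0.49 with hsCRP at 30% vs 30%. With the dependence on the placebo side and a true difference of 25, it gave 23.5 without and 24.3 with. The shift removed is therefore about 0.8 to 1.6 points, either way. Type I error of the CMH across the scenarios run is 5.1–5.8% without the term and 4.9–5.7% with it.

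**Scale.** With complete data at 55% vs 30%, SE = √[(0.55·0.45 + 0.30·0.70)/35] = 11.4 points; with missing data it is about 12. One responder in 35 is 2.9 points.

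**Supportive adjusted risk difference** (pairwise, 35 per arm, π = 30%):

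- 70% vs 30%: power of the CMH vs the adjusted analysis is 92.8% vs 92.8% at gap 0 and 92.7% vs 93.8% at gap 20.
- Variance with vs without hsCRP, π = 20–40%: ratio 1.01–1.02 at gap 0 and 0.97–0.98 at gap 20.

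**The case against.** The strongest objection is that the shift removed is not the same as error removed. In the 5/25% active-arm row, the estimate moves by 0.95 point but the error against the true 25 falls only from 0.52 to 0.43. With 5/25% in both arms the error grows by 0.22. This stands. It arises because imputation also pulls the difference slightly toward zero, by about 0.4–0.7 point in some rows. When hsCRP-related missingness inflates the difference, the two partly offset; when it deflates the difference, they add. In the placebo-side case the error falls from 1.5 to 0.7. A plan cannot rely on the favourable direction.

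It is also fair that prevalence, gap and arm-specific missingness are all assumed. The design limits missing Week 12 data too: subjects who stop drug may stay in visits, and the treatment-policy estimand uses all observed values. The five baseline VAS scores are equally unnamed in the binary model. hsCRP status differs in that it chooses the rule, but that makes it a sensible addition, not a necessity.

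SAP 6.1 does not limit the model to the factors it names, and the redacted Protocol 8.5.2 and SAP 6.5 may contain an hsCRP analysis. A reader might infer that none is planned at all; the documents do not support that.

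**Conclusion.** This is a cheap improvement of low severity. The textual gap is real: the status that selects the criterion is already derived, yet it is not named in the binary imputation model and appears in no unredacted analysis of the primary endpoint. Under 30% prevalence and a 20-point gap, the imputation term removes a shift of about 0.8–1.6 points if missingness depends on hsCRP in one arm only, with a smaller net gain in some cases. Otherwise there is no gain, and possibly a loss of about 0.2 point. The adjusted analysis gains about 1 power point at a 20-point gap and nothing at gap 0.

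Three stronger readings are not supported:

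- **That the primary CMH is invalid or must be stratified by hsCRP.** Randomization protects the test, and simulated type I error stays near 5%.
- **That SAP 3.3 already requires hsCRP in the primary analysis, or contradicts 6.3.1.** The sentence does not name hsCRP and says nothing on how it applies to a binary endpoint tested by CMH. It needs a wording clarification only.
- **That the missing hsCRP subgroup is a defect.** At 20% prevalence there would be 0.20 × 140 = 28 elevated subjects, about 7 per arm, too few for more than a main effect.

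**What to change.** Before unblinding, with the protocol's CMH kept as the primary test:

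1. **SAP 6.1:** add Day 1 hsCRP status (below vs at least 1.5 ULN) as a single main-effect term in the binary imputation model.
2. **SAP 6.3.2:** add one supportive risk difference with confidence interval, adjusted for the two randomization factors and hsCRP status as a main effect (for example, a standardised estimate from logistic regression), with responder counts by hsCRP group.
3. **SAP 3.3, wording only:** say how the covariate sentence applies to the binary endpoint, or limit it to the ESSDAI and ESSPRI models.

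Do not use an 8-stratum CMH, and do not drop the ESSDAI factor to make room for hsCRP.

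The cost is a few sentences and one output. If hsCRP is uninformative, the imputation term costs up to about 0.4 point of power (for example 87.2% to 86.8%) and the supportive analysis has 1–2% more variance. Report the latter as an estimate with interval: its Wald test runs at 5.8–6.2% type I error with an unscaled model-based standard error, and at 5.0–5.4% with the variance scaled by N/(N−p), where p is the number of model parameters.

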1.3. Sample Size and Power

The sample size was estimated based on historical data. Assuming a response rate of 70% for an active arm and 30% for the placebo arm at Week 12, approximately 35 evaluable subjects will be needed in each arm to achieve 85% power to detect a significant difference at a 2-sided, 0.05-level. Enrollment of approximately 35 subjects per arm is planned to ensure that a sufficient number of subjects is available for the analysis of the primary endpoint.

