3.5. Multiple Comparisons

All endpoint tests will be done at the significance level of 0.05 with no multiplicity adjustment in this proof-of-concept study.

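### The primary CMH test may drop the ESSDAI randomisation factor when cells are small: the fallback has no defined trigger, CMH does not need it, and pooling usually costs a little power

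*SAP*

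**What the plan says.** Protocol 8.5.1 sets the primary test without a fallback: "CMH approach adjusting for the randomization stratification factors will be used for the hypothesis testing at the 2-sided 0.05-level". SAP 3.3 describes a stratified 1:1:1:1 randomisation on two binary factors: immunomodulatory drug use at baseline, and the screening ESSDAI hematologic plus biological score (below 2, or 2 and above). That makes four strata. The same section says: "Efficacy endpoints will be evaluated using stratification factors as covariates or stratification variables for analyses".

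SAP 6.3.1 repeats the CMH test on both factors and then adds a condition. If that test is "not appropriate due to small cell counts then the levels of the stratification by ESSDAI scores will be pooled", only immunomodulatory drug use is kept. It goes on: "Each of the three hypotheses will be tested separately at the 2-sided, 0.05-level". SAP 3.5 runs all tests "with no multiplicity adjustment in this proof-of-concept study".

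The SAP does not say how small is small, or whether cells are counted by stratum, by stratum and arm, or by stratum, arm and response. Nor does it say who decides, when, whether under blind, or whether one decision binds all three comparisons. SAP 3.1 fixes analysis-set membership before the blind is broken, but nothing similar covers the strata. SAP 6.6 lists only the added estimands as a change from the protocol.

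**The concern.** The fallback treats small cells as a threat to the CMH test. That is true of a separate chi-square test in each stratum. CMH, however, adds observed minus expected counts over strata before it forms a statistic, so sparse strata do not by themselves spoil it. The rule would then set aside a factor that the trial randomises by, for no gain in validity.

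Two things are at stake. Where the dropped factor predicts response, the pooled test is less powerful and somewhat conservative. And while the trigger is undefined, each drug has two possible primary p-values, and nothing in the SAP says which will be reported.

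**Working it through.** **1. The plan's own figure.** For a two-sided level of 0.05, SAP 1.3 takes responder proportions of 0.70 (active) and 0.30 (placebo) and concludes: "approximately 35 evaluable subjects will be needed in each arm to achieve 85% power to detect a significant difference". The pooled-variance formula is

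n = [z(0.975)·√(2·p̄·(1−p̄)) + z(0.85)·√(p₁(1−p₁) + p₂(1−p₂))]² / (p₁−p₂)².

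With p̄ = 0.5 this is (1.960×0.7071 + 1.036×0.6481)² / 0.16 = (1.386 + 0.672)² / 0.16 ≈ 26.5, so 27 per arm. Power at 35 per arm is Φ[(0.4×√35 − 1.386)/0.6481] = Φ(1.51) = 93.5%, or 88.2% by Fisher's exact test. The stated 35 is therefore larger than 85% power requires. It would match 85.1% at 0.05/3, which is not the stated level. The mismatch is on the safe side and does not affect this point.

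**2. Does CMH need large cells?** In stratum k, with a responders on active, arm sizes n₁ and n₂, m responders in all and N = n₁ + n₂, the statistic is [Σ(a − E)]² / ΣV, where E = n₁m/N and V = n₁n₂m(N−m)/[N²(N−1)]. Only the sums matter. A stratum containing one arm only has a = E and V = 0, so it adds nothing and does no harm. The Mantel–Fleiss check compares ΣE with the smallest and largest possible Σa and usually asks for a gap above 5. For 35 versus 35 at 50% response, ΣE = 17.5, with limits 0 and 35, so the gap is 17.5. This holds even if the two small strata have one subject per arm. At 30% response the gap is 35×0.30 = 10.5. These are values at expected margins, not guarantees for every trial, so the level was also simulated.

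**3. How easily could the trigger fire?** One comparison has 70 subjects. With even strata, 70/4 = 17.5 per stratum, 17.5/2 = 8.75 per arm, and 8.75×0.5 ≈ 4.4 per response cell at 50% response. A rule of any response cell below 5 fired in 99.8–100% of simulated trials.

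**4. Level and power.** One active-versus-placebo comparison was simulated: 35 per arm, uncorrected CMH, no missing data, 200,000 trials per scenario. Assumptions not in the documents: the smaller ESSDAI level holds 50%, 20% or 8% of subjects, and its odds ratio for response is 1, 2 or 4.5. Results with arms balanced within strata:

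| Quantity | Both factors | ESSDAI pooled | Loss from pooling |
|---|---|---|---|
| Type I error | 4.9–5.0% | 3.8–4.9% | – |
| Power, 70% vs 30% (planned) | 92.7–95.4% | 92.5–93.5% | 0.2–2.0 points |
| Power, 60% vs 30% (assumed) | 71.5–77.4% | 70.9–71.9% | 0.5–5.5 points |

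A second simulation (40,000 trials per scenario) went up to an odds ratio of 12 and included a 10% ESSDAI stratum. Type I error with both factors was 4.7–5.2%. The loss from pooling was 0.1–3.0 points at 70% versus 30% and 0.5–11.3 points at 60% versus 30%. The upper ends belong to the odds ratio of 12.

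With arms not balanced within strata (odds ratios up to 4.5), pooling ranged from a 4.5-point loss to a gain of about 0.7 points. The gain appears when the factor is weakly or not prognostic. Pooled type I error was at most 5.0%.

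**5. Choosing late.** Reporting whichever of the two tests is significant gives a type I error of about 4.9–5.4% with balanced strata, and up to about 6–7% without that balance.

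**The case against.** The strongest reply is that little follows at the planned effect. SAP 6.3.1 names in advance both the factor to be pooled and the resulting test, the pooled test keeps its level, and power stays above 92% where 85% was planned. The study is a proof of concept with three unadjusted tests. No document says that the hematologic plus biological score predicts an endpoint built from five subject-reported scales and hsCRP. All of this stands, and it limits the size of the point.

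Some stronger readings are tempting but not supported:
- A reader might infer that pooling can only lose power. That holds in the simulations with balanced arms. Without balance and with a factor that is not prognostic, pooling gains slightly. Some imbalance is possible, because SAP 3.3 lets clinical database values override the IWRS strata.
- A reader might infer that the cells can be seen only after unblinding. The SAP does not define a cell. Stratum totals are baseline data and can be counted under blind; only the reading by arm and response needs unblinded data.
- A reader might infer that the 20 imputed data sets could receive different tests. SAP 6.1 applies the same method to all of them, which largely answers this.
- A reader might see a breach of Protocol 8.5.1. The fallback is still a CMH test on a randomisation factor, and a SAP may add operational detail. What remains is that SAP 6.6 does not list it.

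The reply does not supply a reason for the fallback: sparse strata do not invalidate the test that it replaces.

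**Conclusion.** The point holds as a minor one. The premise that small cells make the two-factor CMH test inappropriate is not borne out, and the trigger is undefined, so the SAP does not settle which test is primary. A common reading of small would make the fallback the default.

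The cost is modest. With balanced arms it is about 0.1–2 points of power at 70% versus 30% for a stratum odds ratio up to 4.5, and about 3 at 12. At an assumed 60% versus 30% it is about 0.5–5.5 points, and about 11 at 12. The pooled test errs on the conservative side when the factor is prognostic. The room for selective choice is small if strata are balanced.

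These sizes rest on assumed stratum shares and prognostic strength, neither of which the documents give, and on complete data. Multiple imputation and Rubin's rule were not simulated.

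**What to change.** Delete the fallback sentence in SAP 6.3.1 and stratify by both randomisation factors in all three comparisons and all imputed data sets. State that a stratum with only one arm contributes zero.

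If a safeguard is still wanted, define it by a numeric threshold on blinded stratum totals. Fix it before unblinding, apply one decision to every comparison and imputed data set, and list it in SAP 6.6.

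Either change takes a sentence or two in the SAP, with no new data or subjects. The downside of always keeping both factors is small: up to about 0.7 points of power if arms prove unbalanced within strata and the ESSDAI factor is not prognostic.
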